#### **BACKGROUND AND BRIEF LITERATURE REVIEW**

Induction of labour (IOL) refers to stimulation of contraction before the spontaneous onset of labour to bring an end to pregnancy when the benefits of giving birth at that time outweigh the risks of the induction process [1]. Labour induction is one of the most frequent medical procedures in pregnant women. It is a major intervention in the normal course of pregnancy with the potential to set in motion a cascade of events, leading to delivery of the baby. Some of the indications for IOL include: post-term pregnancy, ruptured membranes with chorioamnionitis, severe pre-eclampsia, pre-labour rupture of membranes without labour, gestational hypertension, non-reassuring fetal status and various other maternal medical conditions such as hypertension and diabetes [1].

In developing countries like Papua New Guinea (PNG) where maternal and perinatal mortality and morbidity remains high [2],coupled with limited capacity to maintain effective monitoring, prolonging pregnancy in the face of impending complications can result in severe adverse outcomes for both the mother and her baby. It is therefore imperative that IOL forms an essential part of obstetrics care and management in PNG.

The techniques available to induce labour have changed overtime. Current regimes using intravenous oxytocin and prostaglandins have been shown to be effective in inducing labour [3]. Whilst Dinoprostone, a prostaglandin E2 agent, is widely used in industrialized countries and approved by the Food and Drug Administration (FDA)[4], its high cost and instability at room temperature limits its usefulness as a cost-effective agent particularly in developing countries. Furthermore, oxytocin used alone without priming and ripening of the cervix has been increasingly associated with failed IOL and high rates of caesarian section [5]. On the other

hand, misoprostol, a prostaglandin E2 analogue has gained much popularity in the last decade in many developing countries including PNG, as an effective IOL agent. Compared to other prostaglandins, misoprostol has several potential advantages. It is stable at room temperature, inexpensive and can be given via several routes (oral, vaginal, sublingual and buccal).

It is possible that the oral route of administration of misoprostol reduces the risk of severe adverse events such as uterine hyperstimulation and rupture compared to other routes of administration such as the vaginal route. However, currently there is not enough evidence to prove this possibility because of the high rates of heterogenicity between studies comparing the vaginal and oral routes of misoprostol administration [1]. Although a lot of studies comparing the vaginal and oral misoprostol routes of administering misoprostol have been conducted [1, 6], there is still a need for more intervention trials comparing various dose regimens of oral misoprostol. Additionally, there is still a lack of data globally from randomized controlled trials to determine the best dose to ensure optimal safety and efficacy of oral misoprostol [1, 6-8].

In view of these, in the present study, we aim to investigate the safety and efficacy of two different regimens of oral misoprostol as part of a randomized controlled trial at Modilon Hospital in Madang Province.

# **AIMS AND HYPOTHESIS**

## **General aim**

To conduct a 2-year open label randomized control trial to determine the safety and efficacy of two different dose regimens of oral misoprostol in inducing labour in Papua New Guinean women in their third trimester of pregnancy.

# **Specific aims**

- To compare the safety and efficacy profiles of low dose titrated oral misoprostol commencing at 12mcg at baseline compared to a standard treatment regimen commencing at 25mcg.
- To determine maternal labour outcomes in women who undergo IOL with low dose compared to the standard treatment regimen by documenting the proportion of adverse and severe adverse events that may occur.
- To determine perinatal outcomes in the babies of women who undergo IOL with low dose compared to standard dose by documenting the proportion of adverse and severe adverse events that may occur.

#### **Hypothesis**

Misoprostol has the potential to cause dose dependent adverse effects such as uterine hyperstimulation and rupture that may lead to adverse and/or severe adverse labour outcomes. Therefore, the ideal oral misoprostol IOL regimen should be one that utilises a low dose. In the present study, we hypothesis that a regimen commencing with a lower dose of oral misoprostol administered at 12mcg per dose and

gradually increased to a maximum of 50mcg per dose over 24 hours will have a non-inferior efficacy and safety profile in inducing labour compared to a regimen that is administered at 25mcg per dose at baseline and gradually increased to a maximum of 50mcg per dose within 24 hours.

#### **METHODS**

#### **Study Site**

Modilon General Hospital is an established provincial hospital that has well over 3000 deliveries in a year and has an average induction rate of 3-5%. It has an obstetrician, registrars and midwives to assist with the study. It has an operating theater facility that can be used to perform emergency caesarian sections and/or any other operative procedures that may be required to manage patients undergoing IOL.

#### **Study design**

The present study will be an open-label randomized controlled trial. Based on computergenerated block randomization, eligible patients will be allocated 1:1 to the standard treatment group (see Figure 1) or to the low dose oral misoprostol group (Figure 2). Allocated treatments will be concealed in sealed numbered envelopes which will be opened in sequence by study medical or nursing staff and the specified treatment administered.

#### **Oral misoprostol protocol**

A solution of 1mcg/ml is made by dissolving 1 tablet (200mcg) of misoprostol in 200mls of tap water. The solution will be measured and given in titrated doses as per the two different protocol requirements. The misoprostol solution will be kept at the nurse's station at room temperature

and discarded if not completed within 24hrs. Each dose, either commencing 12mls (12mcg/ml) or 25mls (25mcg/ml) will be given at an interval of 2 hours and doses incremented accordingly in the two different arms as outlined in Figures 1 and 2. This is in accordance with WHO recommendations of time-interval between each oral misoprostol dose [9].

## **Standard Treatment Arm**

- 25mls(25mcg) every 2 hours for 4 doses 100mls (100mcg) in 8 hours then
- 50mls(50mcg) every 2 hours for 4 doses 200mls (200mcg) in 8 hours then
- 50mls(50mcg) every 2 hours for 4 doses 200mls (200mcg) in 8 hours

#### Total = 500 mls (500 mcg) in 24 hours

- If no progression in the first cycle, rest for 24 hours, then repeat 50mcg(50mls) every 2 hours for 8 doses
  =400mls(400mcg) in 16 hours.
- If no progression in the second cycle, participants will further undergo Foley's catheterization with the intention to treat as shown in figure 1, while those that are already in labour but needing assistance with contractions may undergo augmentation with oxytocin.

# **Intervention Arm**

- 12mls (12mcg) every 2 hours for 4 doses 48mls (48mcg) in 8 hours then
- 25mls (25mcg) every 2 hours for 4 doses 100mls (100mcg) in 8 hours then
- 50mls (50mcg) every 2 hours for 4 doses 200mls (200mcg) in 8 hours

Total = 348mls (348mcg) in 24 hours

• If no progression of labour, rest for 24 hours, then

Repeat 50mls (50mcg) every 2 hours for 4 doses =200mls(200mcg) in 8 hours

Repeat 50mls (50mcg) every 2 hours for 4 doses =200mls(200mcg) in 8 hours

# Total = 400mls (400mcg) in 16 hours

• If no progression in the second cycle, participants will further undergo Foley's catheterization with the intention to treat as shown in Figure 2 while those that are already in labour but needing assistance with contractions may undergo augmentation with oxytocin.

#### FIRST COURSE OF ORAL MISOPROSTOL

Figure 1: Standard Treatment Protocol for oral misoprostol induction of labour at Modilon Hospital.

Figure 2: Intervention arm for oral misoprostol induction of labour at Modilon Hospital

# **Primary endpoint**

The primary outcome measured would be the proportion of women who have a successful live vaginal delivery without any severe adverse event including: i) failed induction necessitating cesarean section, ii) maternal death, iii) retained placenta, iv) perinatal death, and/or v) neonatal admission to special care nursery.

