# **Secondary endpoints**

Secondary endpoints measured will include the proportion of successful live births delivered vaginally i) within 24 hours, ii) the proportion of mothers requiring Foley's catheterization, iii) the proportion of mothers requiring oxytocin augmentation, iv) Neonatal Apgar scores  $\leq$ 7 at 5 minutes post-delivery, and v) reported maternal and neonatal adverse events at 4 weeks post-discharge.

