# SAMPLE SIZE CALCULATION

If there is a true difference in favour of the experimental treatment of 5%, then 236 patients (118 per treatment arm) will be required to be 90% sure that the upper limit of a one-sided 95% confidence interval (or equivalently a 90% two-sided confidence interval) will exclude a difference in favour of the standard group of more than 5%.

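### The hypothesis names non-inferior efficacy and safety, but the only margin-based test is on one composite of both, so meeting the margin supports a net-outcome claim only

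*Protocol*

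**What the plan says.** The Hypothesis section states a two-part claim: the low-dose regimen "will have a non-inferior efficacy and safety profile in inducing labour". Its rationale is that "Misoprostol has the potential to cause dose dependent adverse effects such as uterine hyperstimulation and rupture". The first specific aim likewise names both safety and efficacy.

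The Primary endpoint section defines one binary outcome, "the proportion of women who have a successful live vaginal delivery without any severe adverse event including" five events. The first is an efficacy failure: "i) failed induction necessitating cesarean section". The second is maternal death, and the rest are "iii) retained placenta, iv) perinatal death, and/or v) neonatal admission to special care nursery".

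The Sample Size Calculation has one margin (5 points), one confidence level (one-sided 95%, equivalently a two-sided 90% interval) and one assumed true benefit (5 points): "then 236 patients (118 per treatment arm) will be required".

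Other parts of the plan look at some elements separately:
- **Secondary endpoints:** live vaginal birth within 24 hours, Foley catheterization, oxytocin augmentation, 5-minute Apgar score, and adverse events at 4 weeks.
- **Specific aims 2 and 3:** maternal and perinatal adverse and severe adverse events, by regimen.
- **Data Analysis Plan:** Poisson regression for adverse-event rates, and Fisher's exact test, two-tailed at 0.05, for proportions.
- **Interim analysis:** committee criteria on drug-related, severe and 4-week adverse events.

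None of these has a non-inferiority margin.

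**The concern.** A claim about efficacy and a claim about safety are two statements. A single proportion that adds both kinds of failure can support only a statement about their sum. If the lower dose produced fewer harms and more failed inductions, or the reverse, one change would offset the other inside the composite. The composite could then meet its margin while one part was worse by more than 5 points.

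The secondary endpoints do not fully fill the gap. The 24-hour endpoint is not final induction success: in both arms the first cycle alone lasts 24 hours, and a rest, a second cycle and Foley catheterization may follow. Overall vaginal delivery, caesarean for failed induction, and the four listed harms taken together are not named endpoints. What is at stake is the wording of the trial's main conclusion, and whether a reader can see which part of the composite produced it.

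**Working it through.** **1. The plan's own figure.** Inputs from the Sample Size Calculation: margin 0.05, true benefit 0.05, one-sided 5%, 90% power. The control success rate is not stated. Assume 90% control and 95% experimental:

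n per arm = (1.645 + 1.282)² × (0.90×0.10 + 0.95×0.05) / (0.05 + 0.05)² = 8.564 × 0.1375 / 0.01 = 117.8, so 118 per arm and 236 in total.

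This reproduces the stated size. Control rates of 89% and 91% give 133 and 104. The point therefore concerns what the test can show, not the arithmetic.

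**2. One offsetting scenario (all rates assumed).** Caesarean for failed induction 5% standard v 11% low dose; other listed failures 8% v 2%. Components are taken as mutually exclusive, with no caesarean for other reasons.

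- Composite success: 100 − 5 − 8 = 87% v 100 − 11 − 2 = 87%, difference 0.
- Vaginal delivery: 95% v 89%, 6 points worse and so beyond the margin.

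With d = low-dose minus standard success, the chance of meeting the margin is Φ((d + 0.05)/SE − 1.645), where SE = √[(p₁(1−p₁) + p₂(1−p₂))/118].

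- Composite: SE = √(0.2262/118) = 0.0438; Φ(0.05/0.0438 − 1.645) = Φ(−0.50) = **0.31**.
- Vaginal delivery: SE = √(0.1454/118) = 0.0351; Φ(−0.01/0.0351 − 1.645) = Φ(−1.93) = **0.03**.

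Exclusivity matters little here. With independent components, composite success is 0.95×0.92 = 87.4% v 0.89×0.98 = 87.2%, and the chance is 0.30.

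**3. Range over other assumed rates.** These are 200,000 simulated trials per row, 118 per arm, Wald 90% interval, 5-point margin, 10% control failure, mutually exclusive components. Entries are standard → low dose, then the share of trials meeting the margin.

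| Efficacy failure | Harm | Composite | Efficacy alone | Safety alone |
|---|---|---|---|---|
| 3% → 8% | 7% → 0% | 60% | 7% | 100% |
| 2% → 8% | 8% → 2% | 36% | 3.5% | 99% |
| 8% → 0% | 2% → 8% | 60% | 100% | 3.5% |
| 3% → 5% | 7% → 0% | 91% | 36% | 100% |
| 5% → 3% | 5% → 2% | 91% | 88% | 97% |

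In the first four rows the parts move in opposite directions and the composite misrepresents one of them. In the last row they move together and there is little conflict. The fourth and fifth rows have the same 5-point composite benefit that the plan assumes, and they lead to different conclusions on efficacy.

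**4. Would the planned test of proportions fill the gap?** It tests for a difference, so a non-significant result does not show non-inferiority. For a true rise in caesarean from 5% to 11% (assumed), exact enumeration gives a two-tailed Fisher p-value of at least 0.05 about 70% of the time at 118 per arm.

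**5. What 118 per arm can show for a component.** With equal observed rates of 5%, the half-width of the 90% interval is 1.645 × √(2×0.0475/118) = 4.7 points, just inside the margin. At 10% it is 1.645 × √(2×0.09/118) = 6.4 points, outside it. With no true difference and 5% rates, 90% power needs 326 per arm for each component, and about 409 per arm for both if they are independent.

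**The case against.** A composite of this kind is a legitimate net-benefit endpoint, and a single efficacy and safety profile can be read as a net outcome. That stands, and it is why the composite need not be replaced.

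Four stronger readings are tempting, and the Protocol does not support them.
- **That it treats a met margin as proof of both claims.** No section says so, and rules for interpreting components may lie in an analysis plan that is not shown. The fault is that the stated hypothesis is wider than the only margin-based test.
- **That the lower dose will move the parts in opposite directions.** The dose-dependent harms it names are hyperstimulation and rupture, and neither is among the five listed events, although the list may be open. Nowhere does it say that the lower dose induces labour less well, and the sample size assumes a benefit for it. Opposite movement is possible, not documented.
- **That a rise in failed inductions would go unseen.** Foley and oxytocin use and 24-hour vaginal birth are separate efficacy measures, and Foley follows failure of the second misoprostol cycle. Such a rise could well show there.
- **That safety is never examined apart from the composite.** The aims, the Poisson analysis and the interim criteria all do so.

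The scenario in step 2 was built to offset exactly, and even then the composite misses the margin about 69% of the time. This is fair, and the figures are illustrations. It remains true that none of the separate measures carries a margin, and that overall vaginal delivery and the grouped harms are not named endpoints.

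**Conclusion.** The point holds in limited form. Meeting the 5-point margin on the composite would show a non-inferior net outcome. It would not establish non-inferior efficacy and non-inferior safety as separate findings, which is what the hypothesis names.

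That conclusion follows from the definitions and needs no assumed rates. The size does need them: 31% v 3% in the worked scenario, a wide gap in other offsetting cases, and almost none when the components move together. The Protocol gives no component rates, so none of these figures is a prediction. The composite and the sample size may stand. The claim and the endpoint list should be brought into line.

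**What to change.** 1. Keep the composite as primary, and state in the Hypothesis and Data Analysis Plan that its conclusion concerns the net outcome.
2. Add two named secondary endpoints, each with a 90% confidence interval for the difference between arms:
   - (a) vaginal delivery, with caesarean for failed induction shown separately from caesarean for other reasons, because a caesarean done for harm is not an efficacy failure;
   - (b) any of maternal death, retained placenta, perinatal death or special care nursery admission.
3. State the rule: separate non-inferiority of efficacy, or of safety, will be claimed only if that component's interval excludes a difference of more than 5 points in favour of standard. Otherwise the claim is limited to the net outcome.

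**Cost:** wording and two more reported comparisons. The occurrence of each event is already needed to score the primary endpoint; the reason for each caesarean must be kept. The sample size does not change. The downside is that component intervals at 118 per arm will often be inconclusive, so the claim will often stay at the net outcome.

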# **Secondary endpoints**

Secondary endpoints measured will include the proportion of successful live births delivered vaginally i) within 24 hours, ii) the proportion of mothers requiring Foley's catheterization, iii) the proportion of mothers requiring oxytocin augmentation, iv) Neonatal Apgar scores  $\leq$ 7 at 5 minutes post-delivery, and v) reported maternal and neonatal adverse events at 4 weeks post-discharge.

# **Inclusion and Exclusion Criteria**

All women who deliver at Modilon Hospital must fulfill the following study criteria prior to enrollment:

- Third trimester singleton pregnancies in women over 18 years old
- Bishops score of less than 6
- Cephalic presentation
- Hemoglobin concentration of more than 10g/dL
- Signed written informed consent

Women excluded will include:

- Twin or multiple pregnancies
- Women under 18 years old
- Unstable or abnormal lie

- Previous caesarian section
- Any high risk mothers needing immediate caesarian section

## **Clinical procedures**

As per our labour induction study protocol, all women will be thoroughly screened to ensure those enrolled fulfill the above mentioned criteria. Baseline clinical data (including sociodemographic information, past obstetrics particulars, BMI) as well as laboratory data will be collected for all women. Haemoglobin will be measured using the coulter counter analyzer (ACT. Diff PAK, Beckman's coulter). Hepatorenal function investigations will be performed if indicated. Urinalysis and baseline glucose investigations will also be performed.

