# DATA ANALYSIS PLAN

Per-protocol pre-specified analyses will include study participants with complete delivery data available to compare primary and secondary outcomes by treatment arms. Two-sample comparisons for normally-distributed variables will be performed using the Student's *t*-test, for non-normally distributed variables by Mann Whitney U-test, and for proportions by Fisher's exact test. Safety and tolerability to determine the rate of adverse events will be assessed from the incidence of symptoms/signs during the in-patient period until discharge and at 4 weeks post-discharge using Poisson regression. Unless otherwise stated, all *P*-values will be two-tailed with 0.05 taken as significant.

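### The primary outcome and secondary proportions i–iv are compared unadjusted although parity and entry Bishop score should be available; adjusting is a cheap improvement, small for the primary endpoint, and not the repair of an error

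*Protocol*

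**What the plan says.** - **Baseline data.** Clinical procedures lists "Baseline clinical data (including sociodemographic information, past obstetrics particulars, BMI" as collected for all women, along with laboratory data. Parity is not named, but it should be obtainable from the obstetric history.
- **Bishop score.** Inclusion and Exclusion Criteria requires "Bishops score of less than 6". The score is therefore assessed before enrolment, over a restricted range. The protocol does not say that the numeric value is kept for analysis.
- **Randomisation.** Study design: "Based on computergenerated block randomization, eligible patients will be allocated 1:1". No stratification factor is stated.
- **Analysis.** Data Analysis Plan: "Per-protocol pre-specified analyses will include study participants with complete delivery data available to compare primary and secondary outcomes by treatment arms", with the comparison made "for proportions by Fisher's exact test". No covariate is named. Adverse events are assessed "until discharge and at 4 weeks post-discharge using Poisson regression", so secondary endpoint v (adverse events at 4 weeks) falls outside the Fisher comparison.
- **Primary endpoint.** It is binary: "the proportion of women who have a successful live vaginal delivery without any severe adverse event".
- **Sample size.** 236 women (118 per arm), a 5-point margin, a true 5-point advantage for the experimental arm, a one-sided 95% limit and 90% power. The control success rate is not given.

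**The concern.** Parity and cervical favourability plausibly predict vaginal delivery, vaginal delivery within 24 hours, Foley use and oxytocin use. As written, the information enters neither the allocation nor the comparison of these proportions. A modest chance imbalance in parity would then pass straight into the estimated difference, which for the primary endpoint is to be judged against a margin of only 5 points. An adjusted risk difference would remove most of that shift and, where the covariates are prognostic, narrow the interval. The stake is precision and the credibility of a single trial's result. Validity is not in question.

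**Working it through.** **1. Reproduce the plan's sample size.** The control rate is unstated, so it was solved for. With unpooled variance, n per arm = (1.645 + 1.282)² × [p₀(1 − p₀) + p₁(1 − p₁)] / (0.05 + 0.05)². With p₀ = 0.90 and p₁ = 0.95 the bracket is 0.0900 + 0.0475 = 0.1375, giving n = 117.8, rounded up to 118 per arm, or 236. Neighbouring control rates do not reproduce it: 0.89 gives 266 in total and 0.91 gives 208. The rates 90% v 95% are used below as the implied design.

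**2. Unadjusted precision.** SE = √(0.1375/118) = 0.0341. Power = Φ(0.10/0.0341 − 1.645) = 90.1%. Expected primary failures: 236 × 7.5% ≈ 18.

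**3. How much parity could explain of the primary endpoint.** The protocol gives no prognostic figures. Assume 45% nulliparous and failure 8 to 12 points higher in nulliparous women. Then R² = s(1 − s)d² / [p(1 − p)], with s = 0.45 and p = 0.075:
- d = 0.08: 0.2475 × 0.0064 / 0.0694 = 2.3%
- d = 0.12: 0.2475 × 0.0144 / 0.0694 = 5.1%

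**4. Effect on primary power.** Multiply the variance by (1 − R²) at 118 per arm:

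| R² | Power |
|---|---|
| 0 | 90.1% |
| 2% | 90.6% |
| 5% | 91.3% |

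The gain is about half a point to 1.2–1.3 points.

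**5. Simulation check.** 4,000 simulated trials per scenario, 90% v 95%, linear-model adjustment for nulliparity, Bishop score and BMI. The moderate scenario has odds ratios of 3 for nulliparity, 1.25 per Bishop point and 1.3 per SD of BMI. The weak and strong scenarios scale these log odds ratios by 0.5 and 1.5.

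| Covariates | Variance reduction |
|---|---|
| Not prognostic | about −1% |
| Weak | about 0% |
| Moderate | about 2% |
| Strong | about 5% |

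At control rates of 70–80%, the moderate and strong scenarios gave about 7–16%. The unadjusted difference was unbiased throughout (0.0012 or less in absolute value).

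**6. Chance imbalance in parity.** SD of the between-arm difference in the proportion nulliparous = √(0.45 × 0.55 × 2/118) = 6.5 points. A 2-SD imbalance (13 points) moves the primary difference by 0.13 × 8 to 0.13 × 12 = 1.0 to 1.6 points, which is 0.30 to 0.46 of the SE in step 2.

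**7. A commoner secondary outcome.** For vaginal delivery within 24 hours, assume 50% success in nulliparous and 80% in parous women. Overall p = 0.45 × 0.50 + 0.55 × 0.80 = 0.665. R² = 0.2475 × 0.30² / (0.665 × 0.335) = 0.100. Parity alone then explains about 10% of the variance, equivalent to about 118/0.90 = 131 women per arm instead of 118. A 2-SD imbalance would move this difference by 0.13 × 30 = 3.9 points.

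**The case against.** The strongest reply is that nothing here is wrong. An unadjusted comparison of randomised arms is valid, no stated figure depends on adjustment, and covariates are often chosen in a statistical analysis plan, which is not at hand. All of that stands, except that this protocol does not leave the method open: it names Fisher's exact test for proportions within its pre-specified analyses. A better choice can therefore be proposed for what is written.

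The second reply is that the primary gain is trivial and rests on assumed prognostic strength. This also stands. A 12-point effect would imply about 2.1% failure in parous and 14.1% in nulliparous women, or about 3 failures among some 130 parous women. That is a strong assumption and a sparse table.

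A reader might infer several stronger claims:
- *The unadjusted result is biased, or chance imbalance is an unprotected risk.* The protocol does not support this. Chance imbalance is already part of the unadjusted standard error and error rate; adjustment would only reduce it.
- *The precision is free.* With about 18 failures there is little to gain, and a slight loss if the covariates do not predict outcome.
- *The primary endpoint would gain 10% of variance (power 92.6%).* The parity assumptions above give 2–5%. Bishop score would have to add as much again, although entry restricts it to below 6.
- *Adjustment makes the test match the margin.* Comparing an interval with the 5-point margin is worthwhile in its own right, and an unadjusted interval would do that equally well.

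**Conclusion.** The point holds in a limited form. The protocol fixes an unadjusted test for the primary outcome and secondary proportions i–iv and states no stratification, while obstetric history and entry Bishop score are available before treatment. Adjustment is a cheap improvement.

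For the primary endpoint it is worth about 0–5% of variance, or from nothing to a little over one power point at 90% v 95%, with about a 1% loss if the covariates are not prognostic. For vaginal delivery within 24 hours it is worth about 10% of variance under the assumed 50% v 80%.

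These sizes rest on assumptions the protocol does not supply: the 90% control rate (inferred from the sample size), 45% nulliparity, and the prognostic effects. It is also inferred that parity can be taken from the obstetric history. The required number of women does not change. The unstated control rate matters more: with 118 per arm, unadjusted power is 65% at an 80% control rate and 53% at 70%, and even R² = 10% raises these only to 69% and 57%.

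**What to change.** In the Data Analysis Plan, prespecify for the primary outcome a risk difference adjusted for parity (nulliparous/parous), for example Mantel-Haenszel or standardised from a logistic model. Add entry Bishop score only if the number of events allows, and state that rule in advance. Compare the two-sided 90% interval with the 5-point margin, and report the unadjusted risk difference as a sensitivity analysis. An adjusted odds ratio would not serve, because the margin is on the risk-difference scale.

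Use the same approach for secondary proportions i–iv. Endpoint v stays under the Poisson regression. In Clinical procedures, name parity and the numeric Bishop score as recorded baseline items.

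The cost is wording and slightly more analysis work. The main downside is sparse strata for the primary endpoint, with about 18 failures expected, so the covariates should be kept to one or at most two.
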